## 1. Full history taking including:

Personal, present, past, family, and surgical histories of the patients will be documented. This includes collecting information about the patient's demographics, current health status, medical history, family medical history, and any prior surgical procedures.

#### 2. Clinical Examination:

A thorough clinical examination of the patients will be conducted to evaluate their general health and assess any physical signs and symptoms related to premature ejaculation or other conditions.

Group A (sildosin 4 mg): intake 2h before intercourse (on demand) at least 6 times intercourse /month for 2 months.

Group B (dapoxatine 60mg): the same like sildosin.

**Follow up** patients will be evaluated by PEP (premature ejaculatory profile) & IELT. (intravaginal latency time) 2 months after start of treatment.

Intravaginal ejaculatory latency time (IELT): normal duration 2.5- 5 minutes. (Waldinger MD, et al .2005).

scores of the Premature Ejaculation Profile (PEP): to evaluate the reliability and validity of the Premature Ejaculation Profile (PEP), The

PEP contains four measures: perceived control over ejaculation, personal distress related to ejaculation, satisfaction with sexual intercourse, and interpersonal difficulty related to ejaculation, each assessed on five-point response scales. (Patrick DL, et al.,2009).

Any side effects of drugs will be recognized and recorded.

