Dapoxetine is a selective serotonin reuptake inhibitor, is the first oral pharmacological agent indicated for the treatment of men aged 18-64 years with premature ejaculation. (N Engl J Med. 2019).

Dapoxetine is the only effective and safe available on-label oral treatment for PE, and its use can result in better quality of life for the patient and their sexual partner. (N Engl J Med. 2019).

Oral dapoxetine 60 mg (administered as needed) was effective in the treatment of men with premature ejaculation, inducing significantly greater improvements. (N Engl J Med. 2019).

Silodosin is a selective alpha-1a adrenergic antagonist used in the therapy of benign prostatic hypertrophy. Silodosin is associated with a low rate of serum aminotransferase elevations and to rare instances of clinically apparent acute liver injury. (N Engl J Med. 2019).

Silodosin inhibits alpha adrenergic receptors present on smooth muscle in the bladder neck and prostate (alpha-1a adrenergic receptors)(N Engl J Med. 2019).

Compared with other  $\alpha 1$ -adrenoceptor antagonists, silodosin appeared to suppress ejaculation in a relatively higher percent of trial participants.

This suppression of ejaculation by silodosin suggested its potential for treating premature ejaculation and it seemed to be more effective for preventing PE than other alpha blockers. (Sato Y, Otani T, et al. 2017).

.

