## **Patients and Methods**

A prospective study will be carried out on 50 patients with premature ejaculation who attending outpatient clinic, urology department, Benha university hospitals over a period of 6 months starting from approval of the institutional ethical committee.

An informed written consent will be obtained from the patients. Every patient will receive an explanation of the purpose of the study and will have a secret code number.

Research results will only be used for scientific purposes. Any unexpected risks appearing during research will be clarified to the participants and to the ethical committee on time.

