## Study design:

Patients who meet the previous criteria will be enrolled in the study.

We randomly assigned 80 outpatients with PPE to two groups , group A (sildosin 4mg) 40 patients and group B (dapoxatine 60mg) 40 patients .

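### The plan compares two named drugs on self-rated, privately observed and reported outcomes, but describes no masking of the patient, the outcome collector or the analyst

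*Combined protocol and SAP*

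**What the plan says.** Under Study design, "We randomly assigned 80 outpatients with PPE to two groups", 40 to silodosin 4 mg and 40 to dapoxetine 60 mg. The section 2. Clinical Examination gives the silodosin regimen as "intake 2h before intercourse (on demand) at least 6 times intercourse /month for 2 months", and then adds "Group B (dapoxatine 60mg): the same like sildosin".

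Follow-up is in the same section: "patients will be evaluated by PEP (premature ejaculatory profile) & IELT. (intravaginal latency time) 2 months after start of treatment". The PEP covers "perceived control over ejaculation, personal distress related to ejaculation, satisfaction with sexual intercourse, and interpersonal difficulty related to ejaculation", "each assessed on five-point response scales". Side effects are to be recorded, with no statement of who elicits them or how. Tolerability is part of the stated aim (Aim of the Work).

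Neither the protocol text nor the Statistical analysis section mentions masking of anyone, a placebo, matched product, plain packaging, or an open-label design with a reason. No outcome assessor is identified. No stopwatch, diary, partner timing or recall is named for IELT.

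**The concern.** Each PEP item asks the man how he feels about control, distress, satisfaction or difficulty. A man who knows his drug can answer partly from what he expects of it. IELT arises in private intercourse, so the figure reaches the investigator through the patient or partner, and no timing method is fixed that would limit the influence of expectation. Side-effect reports depend both on what the man mentions and on what the collector asks.

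Randomisation balances the men at entry. It does not protect outcomes that are rated or elicited afterwards by people who know the allocation. Any difference in reporting between arms is added to the drug effect, and the t-test, Mann-Whitney and chi-square tests in the Statistical analysis section cannot tell the two apart. A significant result could be partly or wholly a reporting effect, and a real difference could be hidden.

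**Working it through.** **Step 1: who could know the allocation when each outcome is produced.**

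| Outcome | Source of the value | Protection described |
|---|---|---|
| PEP, four measures | The man's own rating | None |
| IELT | Patient or partner; method unstated | None |
| Side effects | Reported by the man, recorded by an unnamed person | None |
| Group comparison | Analyst | None |

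**Step 2: is the schedule an obstacle to masking?** No. Timing before intercourse, minimum frequency and duration are the same in both arms. This removes only the timing obstacle; the documents do not describe the appearance of either product.

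**Step 3: how sensitive is the comparison?** The plan gives no effect size, SD or power, so there is no figure of its own to reproduce.

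Inputs:
- n = 40 per arm, from Study design. Patients and Methods says 50 patients in all; assuming an equal split, n = 25 serves as the lower case.
- Significance level 0.05, from Statistical analysis; two-sided is assumed.
- Bias b, the between-arm difference in reporting in SD units. This is an assumption, shown as a range.

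Formula (normal approximation), with no true drug difference:

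SE = √(2/n), in SD units; P(reject) = Φ(b/SE − 1.96) + Φ(−b/SE − 1.96)

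For n = 40, SE = √(2/40) = 0.2236. With b = 0.2, b/SE = 0.894, so P = Φ(−1.066) + Φ(−2.854) = 0.143 + 0.002 = 14.6% (14.55% before rounding the terms).

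| Assumed bias (SD) | False-positive rate, 40 per arm | False-positive rate, 25 per arm |
|---|---|---|
| 0 | 5.0% | 5.0% |
| 0.1 | 7.3% | 6.4% |
| 0.2 | 14.6% | 10.9% |
| 0.3 | 26.9% | 18.6% |
| 0.5 | 60.9% | 42.4% |

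The t distribution gives slightly lower values: at 40 per arm, 14.3% for 0.2 SD and 59.8% for 0.5 SD.

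**Step 4: bias against a real effect.** With 40 per arm, power is about 80% for an assumed true difference d = 0.63 SD: Φ(0.63/0.2236 − 1.96) = Φ(0.857) = 80.4%. Replacing d by d − b gives 65.9%, 48.5% and 31.4% for opposing bias of 0.1, 0.2 and 0.3 SD.

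These figures treat bias as a constant shift on a continuous scale. A five-point item will not follow them exactly. They show sensitivity and do not estimate the bias in this trial.

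**The case against.** The strongest reply is that the plan is silent rather than openly unmasked, and that much of what could be alleged beyond that silence is inference. Several stronger readings are tempting, and the documents do not support them:

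- **That both efficacy measures are the man's own report.** This is certain for the PEP. For IELT the method is not stated; partner timing or a stopwatch is possible, and would be less open to expectation than a rating.
- **That expectation is known to favour dapoxetine.** The Introduction says "Dapoxetine is the only effective and safe available on-label oral treatment for PE" and describes silodosin as a prostate drug that might help. That is background, not text for patients. Patients and Methods says men hear the study's purpose; neither it nor Ethical considerations says they are told that one drug is established and the other is not. Novelty could favour silodosin. Unequal expectation is plausible, but neither its existence nor its direction is shown.
- **That a masking code already exists.** The sentence "Every patient will receive an explanation of the purpose of the study and will have a secret code number" stands among the consent and confidentiality text. It protects identity and does not conceal treatment.
- **That a shared schedule makes full masking simple and cheap.** If the two products look different, plain containers hide nothing once opened. The Introduction also reports that silodosin suppresses ejaculation in some men, so a man may infer his drug.

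The assumed bias has no source in the documents and should carry no weight as evidence of how large the bias is.

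All of this narrows the point without removing it. No document text masks anyone, the outcomes depend on what people report, and no reason is given for leaving masking out.

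**Conclusion.** The concern holds in this limited form: the plan describes no masking, while efficacy and tolerability rest on self-rating, on patient- or partner-supplied IELT and on reported side effects. Bias in either direction would pass into the between-group contrast, and the planned analysis has no means of removing it.

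The size of the bias is unknown. Over the assumed range of 0.1 to 0.5 SD, the false-positive rate would be about 7% to 60% with 40 per arm, and about 6% to 42% with 25. The conclusion does not depend on which sample size is right, although the two must be reconciled. Nor does it depend on showing which drug men expect to work better. It rests on two things: that reporting could differ by arm if the drug is known, and that the plan's silence means no masking is intended.

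**What to change.** Under Study design and 2. Clinical Examination, add:

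1. The pharmacy dispenses each drug out of its branded packaging, in plain coded containers with one common instruction sheet. The patient is not told which drug he has. The pharmacy holds the code list for emergency unmasking.
2. An existing staff member who does not know the allocation collects the 2-month PEP, IELT and side-effect data.
3. The man completes the PEP himself before any interview.
4. The method of measuring IELT is stated and is the same in both arms.
5. Group labels stay coded until the analysis is done.
6. At 2 months each man is asked which drug he thinks he took, and the answers are reported by arm.

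No extra visits, staff posts or patients are needed. The costs are repackaging, a code list and a code-break procedure. Masking will be partial if the products look different or if suppressed ejaculation reveals the drug. Over-encapsulation would be stronger but costs more.

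If patients cannot be masked, the plan should declare the trial open-label, keep the collector and analyst masked, and limit the conclusions on PEP and tolerability accordingly.

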## Aim of the Work

The aim of this study is to assess efficacy and tolerability of Silodosin 4mg vs Dapoxitine 60mg in treatment of primary premature ejaculation.

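### No pre-treatment PEP or recorded baseline IELT is scheduled, so change on the PEP cannot be described and the precision of baseline adjustment is given up

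*Combined protocol and SAP*

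**What the plan says.** The aim is to "assess efficacy and tolerability of Silodosin 4mg vs Dapoxitine 60mg". Two active arms are randomised (Study design) and there is no placebo arm.

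The efficacy assessments appear once, in the follow-up text under Clinical Examination: "patients will be evaluated by PEP (premature ejaculatory profile) & IELT. (intravaginal latency time) 2 months after start of treatment". The same section lists the instrument's content: "PEP contains four measures: perceived control over ejaculation, personal distress related to ejaculation, satisfaction with sexual intercourse, and interpersonal difficulty related to ejaculation". Answers to all four are given on five-point scales. With IELT, that makes five named measures. The plan does not rank them as primary or secondary.

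Two procedures precede treatment. For the first, "Personal, present, past, family, and surgical histories of the patients will be documented", which is described as "collecting information about the patient's demographics, current health status, medical history, family medical history". The second is a clinical examination to "evaluate their general health and assess any physical signs and symptoms related to premature ejaculation or other conditions". Neither names the PEP. The inclusion criteria require IELT below 1 minute and set no PEP score.

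The Statistical analysis section lists the independent-samples t-test, the Mann-Whitney test and the chi-square test. It plans no paired test, change score or baseline covariate.

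**The concern.** A team that follows the plan as written will hold one PEP score per patient, taken after two months on drug. Three things are then out of reach.

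- **Change on the PEP.** The data cannot show whether control, distress, satisfaction or interpersonal difficulty moved in either arm, or in which direction. This matters because there is no placebo arm: if the arms score alike at two months, nothing collected on the PEP shows whether scores improved in both or stayed put in both.
- **Baseline balance.** Nobody can check whether the arms began at similar levels on the four measures.
- **Precision.** The baseline value is usually a useful covariate in a small trial, and it will not be available.

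IELT is only slightly better placed. The entry criterion caps it, so a two-month value above 1 minute implies an increase for that patient. But the plan does not say how IELT is measured at entry, and it does not require the individual value to be kept.

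An analysis plan can be amended later. A score that was not taken before the first dose cannot be recovered.

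**Working it through.** The plan gives no power calculation, standard deviation or effect size, so there is no figure of its own to reproduce. The check has two parts: a reading of the schedule, and an illustration of what the missing baseline costs.

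**Schedule.** Efficacy measures: 4 (PEP) + 1 (IELT) = 5. Scheduled PEP administrations: 0 before the first dose, 1 at two months. A change score needs two per patient, so none can be formed. Scheduled IELT assessments: the entry threshold, with no recorded value required, and 1 at two months.

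**Inputs for the illustration.** Arms of n = 40 (Study design). Alternatively n = 25, from the total of 50 at the start of Patients and Methods, assuming equal groups; the two totals conflict and need reconciling in their own right. Significance level 0.05 (Statistical analysis), taken as two-sided. The baseline-to-two-month correlation r is not in the documents; 0.3, 0.5 and 0.7 are assumed.

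**Precision lost.** Adjusting for baseline multiplies the variance of the between-arm difference by 1 − r², and the interval width by √(1 − r²).

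| r (assumed) | 1 − r² | √(1 − r²) | Interval narrower by |
|---|---|---|---|
| 0.3 | 0.91 | 0.954 | 5% |
| 0.5 | 0.75 | 0.866 | 13% |
| 0.7 | 0.51 | 0.714 | 29% |

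These percentages do not depend on n, apart from the degree of freedom spent on the covariate.

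In terms of power (normal approximation, true difference assumed to be 0.5 SD):

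| | Two-month score only | r = 0.3 | r = 0.5 | r = 0.7 |
|---|---|---|---|---|
| 40 per arm | 60.9% | 65.0% | 73.3% | 87.9% |
| 25 per arm | 42.4% | 45.7% | 53.2% | 69.7% |

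At 40 per arm, the difference detectable with 80% power falls from 0.63 SD to 0.60, 0.54 and 0.45 SD.

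**Chance baseline gap.** The difference between arms in mean baseline score has SD √(2/n), in units of the baseline SD:

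- n = 40: √(2/40) = 0.22
- n = 25: √(2/25) = 0.28

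Only the fraction r of such a gap carries into the two-month difference. At n = 40, in outcome SDs, that is 0.3 × 0.224 = 0.07, 0.5 × 0.224 = 0.11 and 0.7 × 0.224 = 0.16.

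**The gap and the lost precision are one loss.** At n = 40 the unadjusted difference has variance 2/40 = 0.0500 in squared outcome SDs. With r = 0.5, the part due to the baseline gap is 0.25 × 0.0500 = 0.0125 (square root 0.11, as above). The remainder is 0.75 × 0.0500 = 0.0375, which is the adjusted variance. The gap is therefore already inside the unadjusted standard error, and removing it is what produces the narrower interval.

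**The case against.** The strongest defence is that the question is one drug against the other, the arms are randomised, and a comparison of two-month scores needs no baseline to be valid. That stands. A reader might infer from the missing baseline that the comparison is biased, or that chance imbalance is a further harm on top of the lost precision. Neither follows: the comparison is unbiased in expectation, and its standard error already allows for chance imbalance.

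A second defence is that the plan is brief and does not exclude a baseline PEP. Staff might collect one while taking the history. That also stands, so the accurate statement is that the plan does not specify one. But nothing requires it, and an unscheduled score may be missing or taken after dosing.

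Third, a baseline would not settle whether the drugs work. Without a placebo arm, improvement within an arm could reflect expectation or regression to the mean. A reader might infer that adding a baseline would let the trial show that both drugs were effective. It would not. It would show whether, and by how much, scores changed.

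Fourth, the gain may be modest: at r = 0.3 it is only 5%. For IELT, the entry cap restricts the spread of baseline values, which could hold r down. That is a fair limit on the size of the benefit, but not a reason to forgo it at this cost.

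Finally, the stated purpose of the PEP, "to evaluate the reliability and validity of the Premature Ejaculation Profile (PEP", might be read as something a single administration cannot serve at all. That is too strong. One administration can support internal consistency and some construct validity, for example against IELT at the same visit; test-retest reliability and responsiveness need a repeat. The phrase stands next to a citation and may only describe the instrument's source.

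**Conclusion.** The concern holds as an inexpensive improvement that should be made; it does not invalidate the trial. As written, the plan cannot describe change on the four PEP measures in either arm, cannot check baseline balance on them, and gives up a narrowing of the between-arm interval of about 5%, 13% or 29% for r of 0.3, 0.5 or 0.7. IELT shares the gap in part, because only an entry threshold is required.

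That the plan schedules no baseline is certain from the text. The size of the precision loss rests wholly on the assumed r. Treating all five measures as efficacy measures is an inference from the aim and the follow-up text, since no endpoint is ranked.

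**What to change.** In Clinical Examination, state that every patient completes the PEP and has an individual IELT value recorded at enrolment, before randomisation and before the first dose, and again at two months. Say how IELT is measured, and measure it the same way both times.

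In Statistical analysis, specify that the arms are compared on each PEP measure and on IELT with adjustment for that measure's baseline value, for example by ANCOVA. Report within-arm change descriptively only, without presenting it as evidence of drug effect.

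Optionally, reword the purpose of the PEP as comparing the two drugs on its four measures.

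The cost is a short questionnaire and one recorded value, a few minutes per patient at a contact that already takes place. The Study design section describes randomisation in the past tense. If dosing has begun, the change helps only patients not yet treated, and the report should make no statement about PEP improvement in patients who have no baseline score.

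### Tolerability is half of the aim, but there is no standard way of asking, no record of stopping and one scheduled contact, so side effects may be under-recorded and the comparison biased

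*Combined protocol and SAP*

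**What the plan says.** The section Aim of the Work puts the two goals side by side: to "assess efficacy and tolerability of Silodosin 4mg vs Dapoxitine 60mg".

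The section 2. Clinical Examination, under Methods, holds everything operational on this point:

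- Exposure, the same in both groups: "intake 2h before intercourse (on demand) at least 6 times intercourse /month for 2 months".
- Follow-up: "patients will be evaluated by PEP (premature ejaculatory profile) & IELT. (intravaginal latency time) 2 months after start of treatment". No other contact after the start of treatment is scheduled.
- Side effects: "Any side effects of drugs will be recognized and recorded". No question, timing, severity scale, event definition or assessor is given.

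Patients and Methods adds: "Any unexpected risks appearing during research will be clarified to the participants and to the ethical committee on time". Statistical analysis names a chi-square test for qualitative variables, but no tolerability outcome, analysis set or rule for missing data. No section describes masking, a diary, or a record of who stopped treatment and why.

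**The concern.** Two features leave the tolerability comparison exposed.

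The first is what gets recorded. Taken literally, the sentence covers effects of the drugs, so someone has to link an event to the drug before it counts. With no masking described, that link may be made by a person who knows the arm. Any resulting bias could run in either direction.

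The second is who gets asked. A man who cannot tolerate an on-demand drug can simply stop taking it, and may then see little reason to attend an evaluation of ejaculatory latency and control. If he stays away, nothing in the plan prompts anyone to ask about his event or to note that he stopped. Absence is then related to the outcome being measured. If it is commoner in the less well tolerated arm, that arm looks better than it is. A larger sample does not cure this, and events not asked about during the trial cannot be reliably recovered later.

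**Working it through.** The documents state no side-effect rate, dropout rate or power, so there is no planned figure to reproduce. The arithmetic below shows mechanism and range only.

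**Inputs**
- Men per arm, n = 40, from Study design ("We randomly assigned 80 outpatients with PPE to two groups", 40 in each). Patients and Methods says otherwise ("A prospective study will be carried out on 50 patients with premature ejaculation"). The two must be reconciled. The recorded percentages among men seen do not depend on n.
- True side-effect rates, p: 40% and 20% (assumed). That is 0.40 × 40 = 16 affected men and 0.20 × 40 = 8.
- Share s of affected men who stop, are not seen at 2 months and report nothing: 0, 25% or 50% (assumed). Unaffected men are all taken to attend.

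**Formulas**
- Men seen: n(1 − ps)
- Recorded rate among men seen: p(1 − s) / (1 − ps)
- Recorded rate if absent men are counted as event-free: p(1 − s)

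**Results (true difference 20 points)**

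| Affected men lost | Worse arm, among men seen | Other arm, among men seen | Difference | Difference if absent men count as event-free |
|---|---|---|---|---|
| 25% in both arms | 12/36 = 33.3% | 6/38 = 15.8% | 17.5 points | 12/40 − 6/40 = 15 points |
| 50% in both arms | 8/32 = 25.0% | 4/36 = 11.1% | 13.9 points | 8/40 − 4/40 = 10 points |
| 50% in worse arm only | 8/32 = 25.0% | 8/40 = 20.0% | 5 points | 8/40 − 8/40 = 0 points |

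With equal shares lost, both rates are understated and the difference shrinks, but the ordering holds. Near-disappearance of the difference needs strongly unequal loss.

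**A false difference is also possible.** Suppose both true rates are 30% (12 men per arm) and half of the affected men are lost in one arm only. The recorded rates are 6/34 = 17.6% and 12/40 = 30.0%, a spurious 12.4 points in favour of the arm that lost more men. If the shares lost are equal, no false difference arises, but both rates are understated.

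**The choice of denominator matters.** In the last row of the table, the eight absent men move the result from 5 points to 0 according to how they are counted. The plan does not say how.

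**The case against.** The strongest reply is that the plan is loosely worded but not defective, and much of that reply stands.

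- A reader might infer that events not attributed to the drug are excluded by rule. The text does not go that far. It sets no causality step, names no assessor and excludes nothing expressly, and side effects may simply be ordinary wording for adverse events. What stands is that the scope is ambiguous and its literal reading is the narrow one.
- A reader might infer that the plan, followed as written, drops men who stop early. It does not. The opening line of Methods applies what follows to every eligible patient, so a man who stopped the drug is still due his 2-month evaluation. Loss requires non-attendance, which the plan neither prescribes nor predicts. What is missing is any step when it happens.
- A reader might infer that such a man's event can never be captured. The recording sentence carries no time point, so an event volunteered between visits could be noted. The commitment on unexpected risks also presupposes some awareness during the study, but it concerns communication and does not set up data collection.
- The collapse to 5 or 0 points depends on losing half of the affected men in one arm and none in the other, and no document supports that pattern. This is why the equal-loss rows are shown beside it.
- Lack of masking, missing-data handling and an undefined analysis set affect efficacy too. Specific to tolerability are the absence of standard questioning and of any record of stopping.

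**Conclusion.** The concern holds as a gap in data collection. Tolerability is a joint aim, and the plan gives no uniform way of asking about it, no record of stopping or its reason, and no step for men who miss the only scheduled contact. This risks under-recording in both arms and, if loss differs by arm, a biased comparison.

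Confidence is high for the omission, which rests on the text alone. It is low for the size and direction of any bias. Under the assumed rates of 40% and 20%, the recorded 20-point difference could be anywhere from 17.5 points down to 5 among men seen, or down to 0 if absent men are treated as event-free. The documents do not show that men will be lost, that loss will be unequal, or that attribution will favour either drug. The point is therefore a worthwhile and cheap improvement. It is not evidence that the tolerability result will be wrong.

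**What to change.** In 2. Clinical Examination, replace the side-effect sentence with a rule to this effect:

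- At the 2-month evaluation, every randomised man, including any who stopped the drug, is asked about all adverse events with the same fixed checklist in both arms, whether or not an event is attributed to the drug.
- He is also asked whether he took any dose, whether he stopped, when and why. The plan has no intake record, so this question is what makes a dosed population identifiable.
- Men who miss the visit are telephoned and taken through the same checklist. A call at 1 month is optional. A call triggered by stopping would be hard to run, because with on-demand use nothing tells staff that a man has stopped.

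In Statistical analysis, add:

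- Two tolerability outcomes, compared between arms: the proportion with at least one event, and the proportion who stopped because of an event. Both are taken among all randomised men known to have taken at least one dose.
- The number of men not reached in each arm, with a sensitivity range that adds them to the denominator, first all as having an event and then all as not. In the unequal-loss example this range runs from 8/40 − 8/40 = 0 to 16/40 − 8/40 = 20 points, which shows the reader how much rests on the absent men.

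The cost is protocol wording, a short checklist and a few telephone calls. The downside is that recorded event percentages will be higher in both arms, because unrelated events are included. No dose or treatment rule changes. The 50 versus 80 conflict in patient numbers needs reconciling separately, because it sets the tolerability denominator.
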